##### **Medication end date**

- If only day is missing,
  - If month and year match that of last contact date, and the medication was ongoing, then impute the end date to be the last day of the month. Otherwise, impute as last contact date.

- If month and year are prior to the last contact date, then impute as the last day of the month.
- If both day and month are missing,
  - If the year matches that of last contact date, and the medication is ongoing, then impute as December 31st. Otherwise, impute as last contact date.
  - If the year is prior to or after last contact date, then impute as December 31st.
- If the medication end date is completely missing and the medication is ongoing, impute as last contact date.
- In all other cases the incomplete medication end date will not be imputed.

Table 3 and Table 4 provide examples for different scenarios for imputing concomitant medication start and end dates, respectively. The imputation of the start date of prior and concomitant non-drug therapy will follow the same conventions as for concomitant medication start date. However, imputation of non-drug therapy end date will be different, as the data collected on non-drug therapy does not include whether the therapy is ongoing. The imputation of non-drug therapy end date is as follows: completely missing end dates will not be imputed, end dates with only day missing will be imputed to the last day of the month, and end dates with both day and month missing will be imputed to December 31.

**Table 3: Concomitant Medication Start Date Imputation Example Scenarios**

Partial conmed start date	Treatment start date	Temporal relationship compared to treatment start	Imputed Date
12MMMYYYY	20OCT2001	Uncertain	<blank>
DDMMM2000	20OCT2001	Before	01JUL2000
DDMMM2002	20OCT2001	After	01JAN2002
DDMMM2001	20OCT2001	Uncertain	21OCT2001
DDSEP2001	20OCT2001	Before	15SEP2001
DDOCT2001	20OCT2001	Uncertain	21OCT2001
DDNOV2001	20OCT2001	After	01NOV2001

**Table 4: Concomitant Medication End Date Imputation Example Scenarios**

Partial conmed end date	Last contact date	Ongoing	Imputed Date
Missing	20OCT2001	Yes	20OCT2001
DDMMM2000	20OCT2001	No	31DEC2000
DDMMM2002	20OCT2001	No	31DEC2002
DDMMM2001	20OCT2001	No	20OCT2001
DDMMM2001	20OCT2001	Yes	31DEC2001
DDSEP2001	20OCT2001	No	30SEP2001
DDOCT2001	20OCT2001	No	20OCT2001
DDOCT2001	20OCT2001	Yes	31OCT2001

### 7.1.9.2 Adverse Events

The imputation of the start date and end date of AEs will follow the same conventions as for concomitant medication start date and end date.

AEs that are completely missing a start date will be considered as treatment emergent if the end date of the AE is either missing or occurs after the treatment start date. In this case, impute AE start date to be treatment start date.

### 7.1.9.3 Death Date

Missing or partial death dates will be imputed based on the last contact date:

- If the date is completely missing, it will be imputed as the day after last contact date.
  - Note: A special case is the patient’s last contact date is the same as the data cutoff date. In this case, his death date will be imputed as the day after the last contact date. Therefore, he would be still alive as of the data cutoff date.
- If the day or both day and month are missing, death date will be imputed to the maximum of the full (non-imputed) [last contact date (excluding the date of death) + 1] and the following:
  - Missing day: 15th day of the month and year of death
  - Missing day and month: July 1st of the year of death

### 7.1.9.4 Exposure Date

No imputation will be done for start date of treatment. Date of last dose of study drug if unknown or partially unknown will be imputed as follows:

- If the last date of study drug is completely missing and there is no EOT eCRF page and no death date, the patient should be considered to be on-going and the data cutoff date will be used as the last dosing date for the analysis.
- If the last date of study drug is completely or partially missing and there is either an EOT eCRF page or a death date available (within the data cutoff date), then imputed last dose date will be as follows:
  - = 31DECYYYY, if **only Year** is available and Year < Year of min (EOT date, death date)
  - = Last day of the month, if **both Year and Month** are available and Year = Year of min (EOT date, death date) and Month < the month of min (EOT date, death date)
  - = Last day of the month, if **both Year and Month** are available and Year < Year of min (EOT date, death date)
  - = min (EOT date, death date), for all other cases

The imputed date will be compared with start date of study treatment:

- If the imputed date < start date of study drug, then last date of study drug is set to start date of study drug;
- Otherwise, use the imputed date.

#### 7.1.9.5 Date of Initial Diagnosis of Cancer

Incomplete dates of initial diagnosis of cancer will be imputed as follows:

- If only day is missing, impute as the 15th day of the month.
- If both day and month are missing and the year is prior to the year of the first study treatment, impute as July 1st.
- If both day and month are missing and the year is same as the year of the first study treatment, impute as January 1st.
- If the date is completely missing, no imputation will be performed.

#### 7.1.9.6 Dates of Anticancer Therapies

##### Prior therapies:

Incomplete start dates will be handled by applying the same imputation rules as AE/concomitant medications start date except:

- If only day is missing, and month and year match that of the treatment start date, impute as date of first dose of study drug -1;

- If both day and month are missing, and the year matches that of the treatment start date, then impute as date of first dose of study drug – 1;
- Completely missing start date is imputed as date of first dose of study drug – 1.

Incomplete end dates and dates of progression on the prior anticancer therapies will be handled using the following rule:

- If only day is missing, imputed date = min (first dose of study drug -1, last day of the month);
- If both month and day are missing, imputed date = min (first dose of study drug -1, 31DEC);
- Completely missing end dates will not be imputed.

If the end date or the date of progression is not missing, and the imputed start date is after the end date or after the date of progression, use the min (end date, date of progression) as the imputed start date.

### **Subsequent therapies:**

Incomplete subsequent anticancer therapy start dates will be imputed using the following rule:

- Imputed date = max (EOT date + 1, first day of the month), if day is missing;
- Imputed date = max (EOT date + 1, 01JAN), if day and month are missing;
- Impute date = EOT date+ 1 if the date is completely missing.

End of Treatment Date is the date of treatment discontinuation as collected from the disposition eCRF page.

There will be no imputation for missing end dates.

## **7.2 Patient Disposition**

Patient disposition analyses will use the FAS unless otherwise stated.

The following disposition categories will be summarized:

- Number (%) of patients enrolled
- Number (%) of patients enrolled but not treated
- Number (%) of patients who received at least one dose of study drug
- Number (%) of patients who are still on treatment
- Number (%) of patients who discontinued the treatment
  - Primary reasons for treatment discontinuation
- Number (%) of patients who discontinued the treatment but are still in follow-up

- Number (%) of patients who were no longer being followed for study evaluation completion
  - Primary reasons for study evaluation completion

Inclusion and exclusion for each of the analysis sets will also be summarized.

Patient disposition data will also be listed.

Screen failure patients are those who were screened, but never started the study treatment for any reason. The data collected on these patients will not be included in any analyses. A listing of reasons for screen failure will be presented.

A separate listing will describe each patient's inclusion or exclusion status for each of the analysis sets defined in [Section 5.0](#).

### 7.3 Protocol Deviations

Protocol deviations will be determined and documented prior to database lock as outlined in the *Specifications of Protocol Deviations*. The number and percentage of patients in the FAS with any protocol deviations will be tabulated by deviation category, study part and cohort. Protocol deviations will be presented in a data listing.

### 7.4 Patient Characteristics

Patient characteristic analyses will be performed using the FAS.

#### 7.4.1 Demographics and Pretreatment Characteristics

Demographic and other pretreatment characteristics including age, gender, race, ethnicity, height, weight, and ECOG performance status, will be summarized.

A demographics listing by patient will be created.

#### 7.4.2 Medical and Disease History

Summary of disease history will be created including date of initial diagnosis, stage at diagnosis and stage at study entry.

Medical and disease history will also be listed for each patient.

#### 7.4.3 Substance Use

Data on tobacco use and alcohol use as collected on the Substance Use eCRF page will be included in a listing.

CCI

[REDACTED]

- [REDACTED]
- [REDACTED]
- [REDACTED]
- [REDACTED]
- [REDACTED]

[REDACTED]

#### 7.4.5 Prior Anticancer Therapy

Prior anticancer therapy will be summarized for three distinct subtypes - systemic treatment, radiotherapy and surgery. Number (%) of patients who received, separately, any prior systemic treatment, radiotherapy, or surgery will be summarized.

For prior systemic treatment, the following data as collected on the “Prior Systemic Cancer Treatments” eCRF page will be summarized:

- Number of patients with at least one prior systemic treatment
- Total number of regimens (there can be more than one medication per regimen)
- Type of prior treatments
- Indication at the last prior therapy (based on the end date)
- Best response at the last prior therapy (defined as the best response during the last treatment regimen recorded)

Prior systemic treatments will also be summarized by Anatomical Therapeutic Chemical (ATC) class and PT.

For prior anticancer radiotherapy, the following information about *the last radiotherapy* (based on end date) will be summarized: location, intent of the radiation and best response.

For prior anticancer surgery, type of procedure and result of procedure will be summarized.

All prior anticancer therapies will be listed separately for systemic treatment, radiotherapy, and surgery.

Incomplete dates will be handled as described in [Section 7.1.9.6](#).

#### 7.4.6 Other Prior Medications and Procedures

Prior medications (defined as any medications, excluding study drug and prior anticancer treatments) and significant non-drug therapies (including physical therapy, herbal/natural medications, and blood transfusions) recorded in the “Prior and Concomitant Medications” eCRF will be summarized. These medications and therapies will be coded using the World Health Organization Drug Reference Listing (WHO DRL) dictionary that employs the WHO ATC classification system.

The number and percentage of patients will be summarized for medications/non-drug therapies that were stopped prior to start of study drug.

A listing will be produced for medications/non-drug therapies that were stopped prior to start of study drug.

Incomplete dates will be handled as described in [Section 7.1.9](#).

### 7.5 Efficacy Analysis

Efficacy analyses will be performed using the FAS.

#### 7.5.1 Objective Response Rate

ORR is defined as the proportion of patients who have achieved a best overall response (BOR) of complete response (CR) or partial response (PR) as determined by Investigator review of radiographic disease assessments per RECIST v1.1. Both confirmed and unconfirmed ORR will be summarized, but the primary analysis will be based on confirmed responses.

The BOR is defined as the best response recorded from the study start date until progression and will be determined programmatically based on the Investigator’s assessment of tumor response at each time point per RECIST v1.1. Only tumor assessments performed before the start of any subsequent anticancer therapies and not later than 30 days after last dose of study drug will be considered in the assessment of best overall response. Clinical deterioration or clinical progression noted on the End of Treatment Disposition eCRF will not be considered as documented disease progression for the purposes of the ORR calculation.

The confirmed BOR for each patient is determined from the sequence of overall timepoint (lesion) responses according to the following rules below:

CR = at least two determinations of CR at least 4 weeks apart before progression, where confirmation required, or one determination of CR prior to progression, where confirmation not required.

PR = at least two determinations of PR or better at least 4 weeks apart before progression (and not qualifying for a CR), where confirmation required, or one determination of PR prior to progression, where confirmation not required.

SD = an assessment of SD or better > 6 weeks after start of treatment (and not qualifying for PD, PR or CR).

PD = progression  $\leq$  9 weeks after start of treatment (and not qualifying for CR, PR, or SD).

NE (Not Evaluable) = all other cases (i.e. not qualifying for confirmed CR or PR and without SD after more than 6 weeks or early progression within the first 9 weeks).

Patients with confirmed best overall response 'Not Evaluable' will be summarized by reason for having unknown status. The following reasons will be used:

- No baseline assessment
- No adequate post-baseline assessment
- All post-baseline assessments have overall response of "NE"
- New anticancer therapy started before first post-baseline assessment
- SD occurred  $\leq$  6 weeks after the start of treatment
- Progression >9 weeks after the start of treatment (i.e. tumor assessment of PD was >9 weeks after start of treatment and there was no tumor assessment in between)

Special (and rare) cases where BOR is 'Not evaluable' due to both SD occurring  $\leq$  6 weeks after start of treatment and progression > 9 weeks after the start of treatment will be classified as "SD occurred  $\leq$  6 weeks after the start of treatment".

The ORR will be calculated with an exact two-sided 95% CI. The 95% CI will be derived using the Clopper-Pearson exact binomial CI method. In addition, the number and percentage of patients in each BOR category (i.e., CR, PR, stable disease (SD), progressive disease (PD), and Not Evaluable) will be summarized.

A figure for duration of exposure and best overall response (confirmed) will be created.

A waterfall plot will be created to show the best percentage change from the baseline in the sum of longest diameters. Patients with baseline and at least one post-baseline tumor assessment will be included in the waterfall plot.

Individual lesion measurements and overall response assessments per RECIST v1.1 will be listed by patient and assessment date.

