7.2.1 Response Criteria in Solid Tumors

Response to treatment will be measured using RECIST v1.1 ([APPENDIX 5](#)), as assessed by the Investigators. Confirmation of CR and PR will be required by a repeat, consecutive assessment no less than 4 weeks from the date first documented.

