For the Phase 2 prOVCA cohort, a [Simon's 2-stage optimal design \(Simon 1989\)](#) will be used in the MSS/MMR-proficient prOVCA population. The null hypothesis of the true response rate is 15%, versus alternative of 35%. Accrual of patients in Stage 1 will continue until 9 evaluable MSS/MMR-proficient patients have been enrolled, with evaluable defined as having received at least one dose of study drug. The analysis for Stage 1 will not occur until all evaluable patients in Stage 1 have had the opportunity to have at least 2 post-baseline tumor assessments (or have discontinued tumor assessments beforehand). If there are less than 2 responders in these 9 patients, enrollment into this cohort of the study will be stopped. Otherwise, 14 additional patients will be accrued during Stage 2, for a total of 23 patients enrolled in this cohort. The null hypothesis will be rejected if 6 or more responses are observed in 23 patients. With this sample size, the actual Type I error is 9.9%, and the power is 80%. If the null hypothesis is true, the expected sample size is 15 patients, and the probability of stopping enrollment into this cohort of the study early is 60%. Patients who are MSI-H/mismatch repair-deficient (dMMR) will not be included in the Simon's 2-stage analyses and the study will ensure that the sample size requirements are met by enrolling the required number of MSS/MMR-proficient prOVCA patients.

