1.1.5 Response

All patients will have their BEST RESPONSE from the start of study treatment until the end of treatment classified as outlined below:

Complete Response (CR): Disappearance of target and non-target lesions and normalization of tumor markers. Pathological lymph nodes must have short axis measures < 10 mm (Note: continue to record the measurement even if < 10 mm and considered CR). Residual lesions (other than nodes < 10 mm) thought to be non-malignant should be further investigated (by cytology or positron emission tomography [PET] scans) before CR can be accepted. To qualify as CR, CR must be confirmed by repeat disease assessment studies performed no less than 4 weeks after the criteria for response were first met to qualify as CR.

Partial Response (PR): At least a 30% decrease in the sum of measures (longest diameter for tumor lesions and short axis measure for nodes) of target lesions, taking as reference the baseline sum of diameters. Non-target lesions must be non-PD. To qualify as PR, PR must be confirmed by repeat disease assessment studies performed no less than 4 weeks after the criteria for response were first met to qualify as CR.

Stable Disease (SD): Neither sufficient shrinkage to qualify for PR nor sufficient increase to qualify for PD taking as reference the smallest sum of diameters on study.

Progressive Disease (PD): At least a 20% increase in the sum of diameters of measured lesions taking as references the smallest sum of diameters recorded on study (including baseline) AND an absolute increase of ≥ 5 mm. Appearance of new lesions will also constitute progressive disease (including lesions in previously unassessed areas). In exceptional circumstances, unequivocal progression of non-target disease may be accepted as evidence of disease progression, where the overall tumor burden has increased sufficiently to merit discontinuation of treatment or where the tumor burden appears to have increased by at least 73% in volume. Modest increases in the size of 1 or more non-target lesions are NOT considered unequivocal progression. If the evidence of PD is equivocal (target or nontarget), treatment may continue until the next assessment, but if confirmed, the earlier date must be used.

Table 1: Integration of Target, Nontarget and New Lesions into Response Assessment

Target Lesions	Nontarget Lesions	New Lesions	Overall Response	Best Response for this Category also Requires
Target Lesions ± Nontarget lesions				

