CR	CR	No	CR	Normalization of tumor markers, tumor nodes < 10 mm
CR	Non-CR/Non-PD	No	PR	
CR	Not all evaluated	No	PR	
PR	Non-PD/ not all evaluated	No	PR	
SD	Non-PD/ not all evaluated	No	SD	Documented at least once ≥ 6 to 8 weeks from baseline
Not all evaluated	Non-PD	No	NE	
PD	Any	Any	PD	
Any	PD	Any	PD	
Any	Any	Yes	PD	
Nontarget lesions ONLY				
No Target	CR	No	CR	Normalization of tumor markers, tumor nodes < 10 mm
No Target	Non-CR/non-PD	No	Non-CR/non-PD	
No Target	Not all evaluated	No	NE	
No Target	Unequivocal PD	Any	PD	
No Target	Any	Yes	PD	

Note: Patients with a global deterioration of health status requiring discontinuation of treatment without objective evidence of disease progression at that time should be reported as “symptomatic deterioration”. This is a reason for stopping therapy, but is NOT objective PD. Every effort should be made to document the objective progression even after discontinuation of treatment.

For nonrandomized trials, where confirmation of response is required, best overall response can be interpreted as follows:

Table 2: Interpretation of Best Overall Response

Response: First Time Point	Subsequent Time Point	BEST Overall Response	Also Requires
CR	CR	CR	Normalization of tumor markers, tumor nodes < 10 mm
CR	PR	SD, PD or PR (see comment*)	
CR	SD	SD provided minimum criteria for SD duration met, otherwise, PD	
CR	PD	SD provided minimum criteria for SD duration met, otherwise, PD	
CR	NE	SD provided minimum criteria for SD duration met, otherwise NE	
PR	CR	PR	
PR	PR	PR	
PR	SD	SD	
PR	PD	SD provided minimum criteria for SD duration met, otherwise, PD	
PR	NE	SD provided minimum criteria for SD duration met, otherwise NE	
NE	NE	NE	

CR = complete response; NE = not evaluable; PD = progressive disease; PR = partial response; SD = stable disease

* may consider PR providing initial “CR” likely PR on subsequent review – then original CR should be corrected. Recurrence of lesion after true CR is PD.

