## 1.0 INTRODUCTION

This document describes the statistical analyses and data presentations to be performed for the clinical protocol ARRAY-382-201 entitled “A Phase 1b/2 Study of ARRY-382 in Combination with Pembrolizumab, a Programmed Cell Death Receptor 1 (PD-1) Antibody, for the Treatment of Patients with Advanced Solid Tumors”.

This statistical analysis plan (SAP) should be read in conjunction with the study protocol and electronic case report forms (eCRFs). This document has been developed using the protocol Version 5 dated 02 January 2019 and eCRFs dated 13 June 2018. Any further changes to the protocol or eCRFs may necessitate updates to the SAP.

This SAP provides a comprehensive and detailed description of the strategy, rationale and statistical techniques to be used to assess the safety, efficacy, pharmacokinetics (PK) CCI analyses in adult patients with selected advanced solid tumors (Part A/Phase 1b); in adult patients with advanced solid tumors that have progressed on prior PD-1/PD-L1 inhibitors, in adult patients with platinum-resistant ovarian cancer (prOVCA) and in patients with pancreatic ductal adenocarcinoma (PDA) (Phase 2). The purpose of this SAP is to ensure the credibility of the study findings by specifying the statistical approaches for the final analysis of study data. This SAP will be finalized and signed prior to the clinical database lock.

Statistical analyses detailed in this SAP will be conducted using SAS®, Version 9.4 or higher (SAS Institute, Inc., Cary, NC USA). Noncompartmental PK analyses will be performed with Phoenix® WinNonlin® Version 8.0 or higher (Certara USA, Inc., Princeton, NJ). Original sample size calculations for Phase 2 were conducted using R, Version 3.4.3.

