## 6.0 CHANGES FROM THE STUDY PROTOCOL

There are no changes from the statistical analyses described in the study protocol at this time.

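### SAP 7.5.1 confirms a PR with any two PRs at least 4 weeks apart, a looser rule than the consecutive assessment in protocol (Version 4) 7.2.1, and the difference is not declared

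*SAP*

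**What the plan says.** **SAP 7.5.1.** ORR is reported both confirmed and unconfirmed, with confirmed responses primary. BOR is derived by program from the investigator's time-point responses. The PR rule is "PR = at least two determinations of PR or better at least 4 weeks apart before progression". Nothing is said about an SD or NE scan between the two determinations. Both must also fall before any subsequent anticancer therapy and within 30 days of the last dose.

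**Protocol Version 4, 7.2.1.** "Confirmation of CR and PR will be required by a repeat, consecutive assessment no less than 4 weeks from the date first documented".

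**Protocol Version 4, Appendix 5.** Table 2 is introduced by "For nonrandomized trials, where confirmation of response is required, best overall response can be interpreted as follows". It gives PR followed by SD as SD, and PR followed by NE as SD if the minimum SD duration is met and otherwise NE. The prose in 1.1.5 is less strict: "PR must be confirmed by repeat disease assessment studies performed no less than 4 weeks after the criteria for response were first met", without the word *consecutive*.

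**Change control.** SAP 6.0: "There are no changes from the statistical analyses described in the study protocol at this time". SAP 1.0: "This document has been developed using the protocol Version 5 dated 02 January 2019". Protocol 11.1 lets the SAP modify the statistical methods, but major changes to the primary endpoint's definition or analysis must also appear in an amendment.

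**irRR.** SAP 7.5.5 refers to protocol Appendix 6 and also reuses the 7.5.1 derivation. For irPR, protocol 7.2.2 and the Appendix 6 prose require a consecutive assessment; the PR row of Appendix 6 Table A does not.

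**The concern.** The two rules classify the same scans differently, and always in one direction: every patient confirmed by two adjacent PRs at least 4 weeks apart is also confirmed by the SAP, but not the reverse. Because BOR is programmed, no later judgement restores the missing condition.

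Success is declared at 6 of 23 (prOVCA) and 3 of 29 (PDA), so one reclassified patient at the boundary changes the cohort's conclusion. The same patient enters the DOR analysis, which SAP 7.5.2 limits to confirmed responders, with the clock starting at the first isolated PR.

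The pattern needs nothing exotic. Take target-lesion sums of 100 mm at baseline, then 69, 75 and 68 mm. The changes from baseline are -31% (PR), -25% (not PR) and -32% (PR). The rise from 69 to 75 mm is 6/69 = 8.7%, below the 20% needed for progression, so the sequence is PR-SD-PR. One unevaluable scan is enough for PR-NE-PR.

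**Working it through.** **1. Which sequences differ.** Scheduled scans (protocol Table 11, footnote p) fall at Cycle 3 Day 1 = Day 43, Cycle 5 Day 1 = Day 85 and Cycle 7 Day 1 = Day 127, each ±7 days. The shortest on-schedule gap is Day 50 to Day 78 = 28 days, so adjacent scheduled scans always meet the 4-week minimum. The SAP rule was coded as two or more PRs, and the 7.2.1 rule as two adjacent PRs with NE taken to break adjacency. All sequences of PR, SD and NE were then enumerated:

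| Scans | Sequences | Confirmed, SAP | Confirmed, 7.2.1 | Differ |
|---|---|---|---|---|
| 2 | 9 | 1 | 1 | 0 |
| 3 | 27 | 7 | 5 | 2 (PR-SD-PR, PR-NE-PR) |
| 4 | 81 | 33 | 21 | 12 |

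These count patterns, not patients. PR-PR-SD and SD-PR-PR are confirmed under both rules. For CR the gap is narrower, because Table 2 notes "Recurrence of lesion after true CR is PD"; CR-NE-CR is the case that remains.

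**2. The plan's design figures reproduce.** With X1 responders among n1 in Stage 1 and X2 among the n2 = 14 added in Stage 2, P(reject) = Σ over x ≥ r1 of P(X1 = x) · P(X2 ≥ r − x).

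- prOVCA (continue at ≥2/9, reject at ≥6/23): Type I error 0.0990 at 15%, power 0.804 at 35%, early stop 0.599, expected N 14.6.
- PDA (continue at ≥1/15, reject at ≥3/29): Type I error 0.0992 at 4%, power 0.801 at 15%, early stop 0.542, expected N 21.4.

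The plan states 9.9%, 80%, 60% and 54%, and 15 and 21. The designs are not in dispute.

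**3. Ending exactly one response short.** P = Σ over x ≥ r1 of P(X1 = x) · P(X2 = r − 1 − x).

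- prOVCA at 15%, total of 5: 0.2597×0.2056 + 0.1069×0.2912 + 0.0283×0.2539 + 0.0050×0.1028 = 0.0534 + 0.0311 + 0.0072 + 0.0005 = **0.092**. At 25% it is 0.125; at 35%, 0.051.
- PDA at 4%, total of 2: 0.3388×0.3294 + 0.0988×0.5647 = 0.1116 + 0.0558 = **0.167**. At 10% it is 0.183; at 15%, 0.088.

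**4. What one patient changes (exact 95% CI).**

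- prOVCA: 5/23 = 21.7% (7.5 to 43.7), not rejected; 6/23 = 26.1% (10.2 to 48.4), rejected.
- PDA: 2/29 = 6.9% (0.8 to 22.8), not rejected; 3/29 = 10.3% (2.2 to 27.4), rejected.

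**5. Illustration under an assumption.** The documents give no frequency for the pattern. Suppose a fraction q of all patients have it without being strict responders, with q between 0.5% and 2%. A final-stage flip at the null then needs a cohort one short and at least one such patient among its non-responders.

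- prOVCA (23 − 5 = 18 non-responders): 0.0922 × [1 − (1 − q/0.85)^18] = 0.9% to 3.2%.
- PDA (29 − 2 = 27 non-responders): 0.1674 × [1 − (1 − q/0.96)^27] = 2.2% to 7.3%.

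**6. Stage 1.** The Stage 1 analysis waits until evaluable patients "have had the opportunity to have at least 2 post-baseline tumor assessments". With two scheduled scans the rules agree, so a Stage 1 difference needs a patient who already has a third scan (Day 127).

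**The case against.** The strongest reply is that the governing protocol is not in hand. SAP 6.0 speaks about Version 5, so a mismatch with Version 4 does not prove an undeclared departure. This stands: Version 5 has to be checked first.

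Second, a reader might infer that Table 2 settles both patterns. It does not. It lists pairs of time points only, with no three-visit row. Its PR-then-SD and PR-then-NE rows support the stricter reading, but the Appendix 5 prose is satisfied by the SAP rule. The firm conflict is PR-SD-PR against the word *consecutive* in 7.2.1. For PR-NE-PR the protocol is silent on whether NE breaks the sequence.

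Third, a reader might infer that the primary count is left open. It is not: SAP 7.5.1 gives an explicit rule, to be signed before database lock. The fault is that the rule is looser than 7.2.1 without saying so.

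Fourth, a reader might infer that the Type I error exceeds 9.9%. The documents do not support a figure. They give no frequency for the pattern and do not say which confirmation rule the 15% and 4% null rates assume.

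Fifth, unconfirmed ORR and patient listings are planned, so the effect will be visible. That is a real safeguard, but neither decides the primary result.

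Finally, a bare demand for the next assessment at least 4 weeks later would misfire with unscheduled scans, which SAP 7.1.8 generally analyses like scheduled ones. PRs on Days 43, 60 and 85 have adjacent gaps of 17 and 25 days, yet are three straight PRs over 42 days. The wording under the fix allows for this.

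**Conclusion.** The point holds against protocol Version 4: for the primary endpoint, SAP 7.5.1 uses a looser confirmation rule than 7.2.1, and SAP 6.0 does not mention it. On scheduled scans the rules differ only for patients with two PRs separated by SD or NE and no two adjacent PRs. Such patients can only raise confirmed ORR and enlarge the DOR set.

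The number affected is probably small. The 9.2% (prOVCA) and 16.7% (PDA) are probabilities of ending one short after passing Stage 1, with the strict response rate at the null. They limit the chance that a single such patient decides the final result at those rates; an actual change also requires that patient to exist. Clarification is needed before database lock; the design itself needs no change. For irRR, a secondary endpoint, the conflicting wording lies within Appendix 6, and SAP 7.5.5 inherits it.

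**What to change.** 1. Check section 7.2.1 and Appendix 5 of protocol Version 5.
2. If they are unchanged, state in SAP 7.5.1 that a CR or PR is confirmed by a later assessment showing the same or a better response at least 4 weeks after first documentation, with no assessment in between worse than the response being confirmed. Further PRs on unscheduled scans inside 4 weeks then do not undo confirmation.
3. State explicitly whether an intervening NE breaks confirmation.
4. Alternatively, keep the looser rule, declare it in SAP 6.0, and decide under protocol 11.1 whether it is major enough to need an amendment.
5. Either way, report the other version as a sensitivity analysis, with the number of patients whose status differs.
6. In SAP 7.5.5, say which Appendix 6 wording governs irPR.

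The cost is a few sentences and a change to the BOR program, using data already collected. The downside of the stricter rule is that confirmed ORR may fall slightly: one borderline SD reading between two PRs removes a responder, as does one NE scan if NE is taken to break confirmation.
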